14.0 Risks to Subjects

14.1

Physical, psychological, social, cultural, financial, and legal risks, and risks to privacy and/or confidentiality associated with this research are minimal because the probability and magnitude of harm or discomfort anticipated in the proposed research are not greater, in and of themselves, than those ordinarily encountered in daily lives of the general population or during the performance of routine physical or psychological examinations or tests.

These include:

1. Possible breach of patient privacy and/or confidentiality
2. Possible breach of the security of patient and provider online data
3. Possible patient discomfort due to completing psychological questionnaires
4. Possible patient and provider discomfort due to having therapy sessions audio recorded

14.2

N/A

14.3

N/A

15.0 Potential Benefits to Subjects or Others

15.1

Potential direct benefits to participants assigned to the CBT+Adhere.ly condition include access to a clinically useful health IT resource, gains in patient knowledge and skill, and better patient outcomes.

15.2

Researchers and the general scientific community will benefit from the knowledge gained from the study. This includes knowledge about how to design and implement a user-centered and stakeholder-informed program that supports patient and provider adherence to evidence-based practice as well as effective vs. less effective strategies for implementing health IT solutions that promote this adherence in mental health practice settings in the community.

16.0 Data Management and Confidentiality

16.1

Aim 1 Data Analysis

Focus group transcripts will be coded by trained study staff in NVivo using a hybrid inductive-deductive, consensus-based content analysis,⁵²⁻⁵⁴ and the mCFIR tool.^{36,37,55} Coders will meet regularly to ensure consistency with code definitions and resolve inconsistencies via discussion to achieve consensus. Data aggregation queries will be used to create case memos and assign ratings for mCFIR constructs. Survey data will be analyzed to describe provider goals, challenges, affordances, and constraints. We will use the Expert Recommendations for Implementing Change (ERIC) matching tool to generate a list of potential implementation strategies for refinement.^{56,57} We will synthesize qualitative and quantitative findings to prioritize new features, exercises, and I/S strategies.

Aim 2 Data Analysis

Feasibility

We will assess feasibility of the proposed trial methodology using the following benchmarks, which were informed by the sample size needed for hypothesis testing in Phase II and expert recommendations.⁵⁸⁻⁶¹

Benchmarks: 50 providers will be enrolled in months 1-2 [20/month]); 60 patients will be enrolled in months 2-6 [8/month]); 70% of providers and patients will use Adhere.ly; 70% of session recordings will be uploaded; 70% of weekly HRS II assessments will be completed; 70% of patients will be retained at 3-month follow-up.

Evaluation

The small sample size prevents any conclusions about effectiveness; however, ANCOVA will be used to preliminarily assess-between group differences in clinical outcomes while co-varying for pre-treatment scores. ANOVA will be used to compare homework use and adherence. We also will preliminarily examine relations among study variables (therapeutic alliance, satisfaction).

Implementation

Interview transcripts will be coded by trained study staff in NVivo using the mCFIR

coding scheme developed during Aim 1. Data aggregation queries will be used to create case memos and assign ratings for mCFIR constructs, which we will examine between pre- and post-implementation using a modified CFIR matrix template. We will further synthesize qualitative with quantitative (i.e., mCFIR, RE-AIM) results to confirm and/or explain summative evaluation findings.

Table 2. RE-AIM outcomes

Dimension	Results
Reach	Number of potential providers and patients available for recruitment; percentage eligible/ineligible, invited, and enrolled; sample characteristics; reasons for ineligibility and varying levels of engagement; ambiguities regarding eligibility criteria
Effectiveness	Attrition and related patient characteristics; adverse events; satisfaction; impact
Adoption	Estimated number of settings for future trials; settings and stakeholder characteristics
Implementation	Percentage of providers and patients who use Adhere.ly; average number of exercises used by providers and patients; percentage of session recordings uploaded; percentage of weekly HRS II completed; degree of use and adherence; provider/patient time costs; patient retention; assessment time burden; completed assessments; missing items; broken/lost/stolen equipment; technical issues
Maintenance	Clinical outcomes at 3-months post-baseline

16.2

All data collected during the trial will be securely stored in a REDCap database, including informed consent/assent documents, questionnaire data, and audio recordings. Data obtained from Adhere.ly platform for the purposes of this study will include names, phone numbers, and email addresses, and usage data relating to providers practicing, assigning, and assessing exercises, and patients completing those exercises. These data will be downloaded from Adhere.ly and merged with the data in REDcap. Only IRB-approved and trained study personnel will have access to the REDCap project and access will be limited to information and modules that are required for them to complete their assigned study-related tasks. All identifiers will be marked as such in REDCap and will not be included in the final exported dataset, which will instead include assigned ID numbers.

We will use the following security measures to protect data sources:

1. all research data exported from REDCap will include ID numbers only
2. the codes that link the name of the participant and the study ID will be kept confidential in REDCap
3. computers and servers containing data will be password-protected to prohibit unauthorized access
4. online survey data collection will be accessible only by IRB approved study staff with secure logins
5. Adhere.ly includes state-of-the-art technical infrastructure—including encryption and other software, security practices, and business operational practices to ensure compliance with all major governing legislation, including HIPAA
6. all study data will be kept on a secure, USF server

16.3

We will use the following quality assurance measures for subject recruitment, enrollment, enrollment targets, and for the validity and integrity of the data:

1. study staff will complete and maintain up-to-date CITI and GCP training
2. study staff will be trained and supervised weekly by the PI

3. Standard Operating Procedures (SOPs) will be used to train all study staff
4. a Manual of Procedures (MOP) and study checklists will be used to ensure fidelity to the study protocol
5. informed consent will be obtained and documented by study staff to provide an audit trail
6. any contact with study participants or potential study participants will be documented to provide an audit trail
7. participant screening, recruitment, enrollment and enrollment targets, and data collection will be tracked to provide weekly updates to the PI
8. assessment data will be entered directly by participants into REDCap
9. automated validity checks will be in place for any data collection
10. data checks for ranges, cross-validity, and completion will be completed proximal to data collection
11. collection of any study data will be documented by study staff to provide an audit trail
12. coders will be trained and appropriate measures will be used to assess interrater reliability
13. coders will be blinded to study aims and hypotheses
14. the USF Conflict of Interest (COI) Office will maintain and monitor study progress according to ongoing conflict of interest management plans to ensure compliance with all requirements

16.4

Identifiable information in this study will include provider, patient names, phone numbers, email addresses, and physical addresses. Human subjects research records, including the original signed and dated consent documents, will be stored for at least 5 years after study completion. Signed and dated HIPAA authorizations and consent documents that include HIPAA authorizations will be stored for at least 6 years after study completion. After this time data will be deleted from REDCap. Patient assessment data will be shared with providers upon request, as stated in the consent.

16.5

 Obtaining Signed Authorization	 Waiver of HIPAA Authorization for Recruitment/Screening Purposes Only
 Obtaining Online or Verbal Authorization (Alteration of HIPAA Authorization)	 Waiver of HIPAA Authorization for Entire Study
 Data Use Agreement	 Business Associate Agreement

Patient PHI that will be disclosed to providers will include total scores on questionnaires if patients indicate their permission to do so on the consent form. Patient PHI that will be obtained from providers will include names, session dates, audio recordings of sessions, telephone numbers, and email addresses. We will document in REDCap events where PHI is disclosed or obtained.

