5.0 Procedures Involved

5.1

Aim 1. Understand and prioritize key stakeholder goals, challenges, affordances, and constraints

Aim 1 of this study will use an exploratory sequential (qual→quant) mixed-methods design to conduct semi-structured focus groups (qual) with mental health patients, providers, and administrators and a survey (quant) with providers. We will conduct 4 focus groups per stakeholder group (patient, provider, administrator) and each focus group session will include up to 6 participants. Half of the focus groups will consist of stakeholders from public healthcare institutions and the other half will consist of stakeholders from private healthcare institutions. We then will enroll 100 providers to complete the survey. Analyses will inform the design of new Adhere.ly features and exercises and an implementation/sustainment (I/S) blueprint.

Aim 2. Optimize, preliminarily evaluate, and implement Adhere.ly in community practice settings

Aim 2 of this study will use a randomized controlled OEI Hybrid trial design. The trial will include 50 community mental health providers randomized within their respective practice locations to administer CBT+Adhere.ly (n=25) vs. CBT alone (n=25) to a total of 60 treatment-seeking adult mental health patients with clinically elevated anxiety and/or depression-referred and treated by providers. Study staff will conduct pre- and post- implementation assessments remotely with providers and will facilitate web-based administration of baseline and 3-month post-baseline assessments with patients via REDCap. Treatment sessions may be audio recorded and uploaded to REDCap by providers and coded by study staff to assess provider assignment and assessment of homework. Clients will have the option to allow providers to audio-record their therapy sessions through the consent. Patient homework adherence will be assessed weekly the day of their next session using a REDCap survey, a link to which will be sent via automated text-message and/or email reminders, or by telephone after 1 day of no response.

5.2

 Audio/Video Recording	 Psychophysiological Recording
 Behavioral Interventions	 Record Review - Educational
 Behavioral Observations and Experimentations	 Record Review - Employee

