We will leverage research-practice partnerships established in Aim 1 to recruit 50 master's-level mental health providers and will recruit additional providers via emails to mental health providers registered with doxy.me, if needed. Providers will be contacted by study staff via telephone and/or email to inform them about the study and inquire about their interest in participating. Providers who express interest in participating in the study will be scheduled for a 60-minute, televideo-based consent and training process with study staff to discuss the study, referral procedures, audio recording sessions, and uploading recordings to REDCap. Signed informed consent from providers will be obtained by study staff via REDCap e-Consent. Afterwards providers will complete a

demographics questionnaire and the Attitudes Toward Homework Questionnaire (ATHQ).¹²

Recruitment of patients

We will recruit 60 treatment-seeking adults over 18 with clinically elevated anxiety and/or depression. Patients will be referred and by providers following their initial intake session with that provider. We will ask providers to refer 3-4 patients to maximize the likelihood of treatment completion with at least 3 patients. Providers will receive automated weekly emails with reminders to make referrals and links to a REDCap referral form. Providers will also be able to provide referral information via telephone or email if preferred. If patients express interest in the study, providers will assist them in completing the referral or obtain verbal consent to submit their referral information.

Upon receiving a referral, study staff will contact patient within one working day to provide study information, assess eligibility, obtain signed informed consent from patients via REDCap e-Consent, and assist patient in completing baseline assessments. Study staff will assess eligibility by: (1) administering a phone screen to the patient; and (2) emailing or texting patient a link through the REDCap system to a survey that will include a brief demographic questionnaire, the Generalized Anxiety Disorder-7 (GAD-7) or Patient Health Questionnaire-8 (PHQ-8).⁴⁰⁻⁴² Patients who are eligible, as indicated by a score ≥ 10 on the GAD-7 or PHQ-8, will then provide informed consent via REDCap e-Consent, and complete the remaining study baseline questionnaires.

Treatment

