Providers will be randomly assigned to administer either CBT alone (n=25) or CBT+Adhere.ly (n=25). All providers will be asked to administer CBT as they usually would for each patient, either in-person or via telemedicine, with CBT+Adhere.ly providers integrating Adhere.ly into treatment with their patients. To minimize risk of CBT alone (i.e., “control”) providers being less motivated to refer cases, providers will be informed of their assignment only after their first study-eligible patient has been enrolled. Each provider will be asked to treat 3 patients over the course of 3 months. Providers will be asked to audio record their treatment sessions using either audio recorders provided by the study team, or audiorecording software on their computer, if preferred. Clients will have the option to audio record the treatment sessions through their consent. Providers will be asked to upload those recordings to REDCap either weekly or bi-weekly. Providers will receive automated weekly emails with a reminder to upload audio recordings and a link to a REDCap form for uploading recordings. This form will ask the provider to enter their name, the name of the patient being treated, the session number, and whether the session was conducted in-person or over telemedicine. Providers who have not uploaded a recording after 2 weeks will receive a follow-up phone call from study staff to provide reminders and assistance where needed.

Assessment Strategy and Measures

Trial questionnaires are shown in Table 1. Baseline and 3-month post-baseline questionnaires will be completed by patients via REDCap surveys. Study staff will email or text patients a link to the survey through the REDCap system and will be available to

remotely assist patients in completing questionnaires. As stated previously, GAD-7 and PHQ-8 will be administered to screen potential participants for eligibility criteria and will be administered prior to obtaining informed consent. The informed consent document will specify that these data will be included with participants' study data if they are eligible and agree to participate or will not be included if they are ineligible or decide not to participate.

Table 1. Assessment Measures for Trial

Domain	Informant	Measure	Time Point	
			B	3M
Demographics	Provider	Provider Demographics Questionnaire	✓	
	Patient	Patient Demographics Questionnaire		
Attitudes Toward Homework	Provider	Attitudes Toward Homework Questionnaire (ATHQ) ¹²	✓	✓

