8.0 Study Timelines

8.1

Aim 1. Adult mental health patients, providers, and administrators will participate in one ≤90-minute focus group. Providers will be invited to complete a ≤15-minute survey.

Aim 2. Providers will participate in one \leq 60-minute consent and training process and twelve \sim 60-minute therapy sessions per study case. Study referral procedures will take an additional 5 minutes per patient. An additional 5 minutes per patient, per session will be required to upload audio recordings. Providers who participate in post-implementation interviews will spend an additional 45 minutes in the study. In all, the total amount of time spent in the study will be approximately 28 hours over the course of 9 months, only 4 hours of which will be spent engaging in study procedures beyond their everyday practice.

Patients will participate in a \leq 60-minute eligibility screening, consent, and baseline assessment process. Patients will participate in twelve \leq 60-minute therapy sessions, engage in twelve \sim 10-minute homework assignments, and spend \leq 5 minutes each week completing homework assessments. 3-month follow-up assessments will take \leq 30 minutes. Patients who participate in post-implementation interviews will spend an additional 30 minutes in the study. In all, the total amount of time spent in the study will be approximately 17 hours over the course of 6 months, only about 5 hours of which will be spent engaging in study procedures beyond the time they would have otherwise been receiving therapy from their provider.

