11.0 Local Number of Subjects

11.1

N=282

Aim 1 focus groups: n=24 patients; 24 providers; 24 administrators

Aim 1 survey: n=100 providers

Aim 2 trial: n=50 providers; 60 adult patients

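### Providers are randomised within practice location, but the between-arm ANCOVA and ANOVA in 16.1 have no provider or location term, and the ANOVA has no stated unit of analysis

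*Combined protocol and SAP*

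**What the plan says.** **Randomisation.** Section 5.1 (Aim 2) has "50 community mental health providers randomized within their respective practice locations to administer CBT+Adhere.ly (n=25) vs. CBT alone (n=25" in the second arm. Section 5.2 (Treatment) also assigns the arm to the provider.

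**Patients per provider.** Section 5.2 (Treatment): "Each provider will be asked to treat 3 patients over the course of 3 months". Section 5.2 (Recruitment of patients): "We will ask providers to refer 3-4 patients to maximize the likelihood of treatment completion with at least 3 patients". Section 11.1: "Aim 2 trial: n=50 providers; 60 adult patients". Section 2.1 gives 30 providers and, in the same sentence, arms of 25 and 25. Section 8.1 puts a provider's time at "approximately 28 hours over the course of 9 months, only 4 hours of which will be spent engaging in study procedures".

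**Outcomes.** Homework use by providers and homework adherence by patients are the stated targets and are assessed weekly (2.1, 5.2). Homework use is the HAACS, coded from recordings of the provider's own sessions. Adherence is the patient-reported HRS II. Clinical outcomes are measured at baseline and 3 months.

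**Analysis (16.1, Evaluation).** "ANCOVA will be used to preliminarily assess-between group differences in clinical outcomes while co-varying for pre-treatment scores". Then: "ANOVA will be used to compare homework use and adherence". Nothing else is said on the between-arm comparison of these outcomes.

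**Change of provider.** Sections 9.3 and 13.1 let a patient move to another enrolled provider after re-consent. They do not limit this to the same arm and do not say under which provider the patient is analysed.

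**The concern.** Patients of one provider share that provider's skill, habits and case mix, and weekly records of one patient resemble each other. The arm is assigned to the provider. A test that counts patients or sessions as independent therefore understates the standard error of the arm difference. Practice location is the randomisation stratum, and it is left out as well.

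For the clinical outcomes, an ANCOVA with only the baseline score reads most naturally as a patient-level analysis. For the homework outcomes the unit could be the session or week, the patient, or the provider. These choices give very different error rates, so the gap there is under-specification, not a demonstrable error.

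At stake is whether the reported preliminary comparisons carry correct intervals and p-values.

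**Working it through.** The documents give no ICC, alpha or design effect, so there is no statistical figure to reproduce. A two-sided 5% test and all ICCs below are assumptions.

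**1. Patients per provider.** The sections imply three loads.
- Totals in 11.1: 60/50 = 1.2.
- Hours in 8.1, for two patients: therapy 2 x 12 = 24 h; study time 60 + 2x5 + 2x12x5 + 45 = 235 min = 3.9 h; total 27.9 h. This matches the stated 28 h and 4 h. The same sum gives 17.5 h at 1.2 patients and 41 h at 3. The 30 providers in 2.1 also imply 60/30 = 2.
- Request in 5.2: 3. Since 3 x 50 = 150 exceeds 60, this load fits only if about 60/3 = 20 providers contribute.

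**2. Patients as the unit.** Design effect DE = 1 + (m - 1) x ICC, with m the size-weighted load. Actual type I error = 2 x [1 - Phi(1.96/sqrt(DE))]. For 50 providers, take 40 with one patient and 10 with two: m = (40x1 + 10x4)/60 = 1.33.

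| Load | DE at ICC 0.05-0.20 | Type I error |
|---|---|---|
| 1.2 (m = 1.33) | 1.02-1.07 | 5.2-5.8% |
| 2 | 1.05-1.20 | 5.6-7.4% |
| 3 | 1.10-1.40 | 6.2-9.8% |

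Simulated ANCOVAs agree. Over full retention and the benchmark "70% of patients will be retained at 3-month follow-up", with location variance 0-0.10 and locations of 2-6 providers, they gave 4.6-5.7%, 4.9-7.8% and 5.2-10.1%.

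**3. Sessions as the unit (homework outcomes).** At the 70% upload benchmark, s = 12 x 0.70 = 8.4 sessions per patient, or 60 x 8.4 = 504 records. DE = 1 + (s - 1) x r + (m - 1) x s x ICC, with r the within-patient correlation and m the average load.
- 1.2 per provider, both 0.1: 1 + 0.74 + 0.17 = 1.91, error 16%.
- 3 per provider, both 0.1: 1 + 0.74 + 1.68 = 3.42, error 29%.
- 1.2 per provider, both 0.3: 1 + 2.22 + 0.50 = 3.72, error 31%.
- 3 per provider, both 0.3: 1 + 2.22 + 5.04 = 8.26, error 50%. The 504 records are then worth 504/8.26 = 61.

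Simulation with 8 sessions per patient gave 17%, 27%, 33% and 50%.

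**4. Providers as the unit.** A simulated ANOVA on one mean per provider gave 4.4-5.7% in every setting.

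**5. Omitted location.** Where each location holds several providers in both arms, location variance cancels from the arm difference but stays in the residual. With no provider clustering, DE is about 1 - rho, which gives 4.4%, 3.9% and 2.8% at a location share rho of 0.05, 0.10 and 0.20 (conservative). In a solo practice location and provider coincide, so location variance adds to clustering. Simulated patient-level test, 20 providers x 3 patients, provider variance 0.10, location variance raised from 0 to 0.10: with locations of four, 7.7% goes to 7.2%; with 70% of providers solo, 7.6% goes to 8.9%.

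**The case against.** The strongest reply is that little hangs on these tests. Section 2.2 says the trial is not powered to test hypotheses, and 16.1 says the sample is too small to conclude on effectiveness and calls the comparison preliminary. No benchmark or decision rule uses them. At the stated totals the clinical ANCOVA is close to nominal, so there the fix costs precision for little gain in error rate. A provider-level ANOVA fits the wording of 16.1 and has no clustering error. All of this stands and limits the severity. It does not remove the gap: 16.1 still commits to the comparisons, and lack of power does not make a wrong standard error right.

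Two stronger readings are tempting, and the documents support neither.

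- *Homework use is the most exposed outcome.* HAACS scores the provider's own behaviour, so a reader might infer this. But the documents give no ICC, and the ranking follows from the variances assumed. With provider, patient and session variances of 0.40, 0.10 and 0.50, patient means give about 8%, 13% and 21% error at 1.2, 2 and 3 patients per provider. On the patient mean, however, that provider share is 0.40/(0.40 + 0.10 + 0.50/8.4) = 0.71, far above the 0.05-0.20 used for clinical outcomes. The order can also reverse: in a session-level analysis at 1.2 per provider, adherence with r = 0.5 and provider ICC 0.05 has DE 4.78, against 3.72 for homework use with both at 0.3.
- *Leaving out location offsets leaving out provider.* This holds only where locations contain several providers. In the background survey in 3.2, 70% of respondents were in individual practice. That is a different sample from the trial's providers, but it shows that solo practice cannot be ruled out.

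**Conclusion.** The point holds as a gap in specification. The randomised unit and the stratum are absent from the planned between-arm analyses, and the unit of the homework ANOVA is undefined. The size runs from negligible (patients as the unit at 1.2 per provider), through about 6-10% at 3 per provider, to about 16-50% if sessions are the unit. It is nil for a provider-level analysis. These figures rest on assumed provider ICCs of 0.05-0.20 for patient outcomes and 0.1-0.3 for session records, and on a load that the documents state inconsistently. Which outcome is most exposed cannot be settled from the documents. The consequence is confined to the validity of the reported preliminary comparisons; the feasibility conclusions are untouched. Severity is minor to moderate.

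**What to change.** In 16.1, make the provider the unit of inference for every between-arm comparison, by one of two routes.

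1. A linear mixed model with arm, baseline score where available, practice location, a provider random intercept, a patient random intercept for weekly records, and small-sample degrees of freedom.
2. An analysis of provider means (weekly values averaged within patient, then within provider) with mean baseline score where available and practice location. State that unweighted provider means estimate the provider-average effect, not the patient-average effect.

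Under either route, pool sparse or single-provider locations into one stratum, and say that this is an analysis stratum which 5.1 does not describe.

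For patients who change provider, analyse patient outcomes by the arm of the enrolment provider, and attribute HAACS scores to the provider who delivered the session.

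Reconcile the provider count (30 in 2.1 against 25 + 25 there and 50 elsewhere) and the patients per provider (1.2 from 11.1, 2 from 8.1, 3 from 5.2).

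**Cost.** Wording only; no new data. In simulation, provider means with location held type I error for clinical outcomes at 4.5-5.4%, and intervals widened by about 2-13%, 5-19% and 13-33% at 1.2, 2 and 3 patients per provider (ICC 0.05-0.20, location variance 0-0.10, locations of 2-6 providers, full or 70% retention). The upper ends rise to about 14%, 20% and 40% if the ICC is a share of total rather than baseline-adjusted variance. The mixed model, simulated at location variance 0.05 and ICC 0.05 and 0.20, gave 3.1-5.7% error and widening of 4-10%, 9-14% and 16-27%. Part of the widening at 2-3 patients per provider only restores standard errors that were too small.

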2.0 Objectives

2.1

The purpose of this study is to expand Adhere.ly (<https://adhere.ly/>)—a web-based platform to improve provider implementation and patient engagement in homework (i.e., between-session practice of skills learned during therapy) during mental health treatment—to include new features and therapeutic exercises for adult patients, develop a plan for its implementation and sustainment, and preliminarily evaluate it by conducting a feasibility Optimization, Effectiveness, and Implementation (OEI) Hybrid trial.

Aim 1. Understand and prioritize key stakeholder goals, challenges, affordances, and constraints

We will use an exploratory sequential (qual→quant) mixed-methods design to conduct semi-structured focus groups (qual) with mental health patients, providers, and administrators and a survey (quant) with providers. We will conduct 4 focus groups per stakeholder group (patient, provider, administrator) and each focus group session will include up to 6 participants. We will enroll 100 providers to complete the survey. Analyses will inform the design of new Adhere.ly features and exercises and an implementation/sustainment (I/S) blueprint.

Aim 2. Optimize, preliminarily evaluate, and implement Adhere.ly in community practice settings

We will conduct a small-scale feasibility OEI Hybrid trial with 30 community mental health providers randomized to Cognitive Behavioral Therapy (CBT) alone (n=25) vs. CBT+Adhere.ly (n=25), and 60 treatment seeking and provider-referred adult patients with clinically elevated anxiety and/or depression (outcomes), which we will assess at baseline and 3-months post-baseline. We will assess homework use by providers and adherence of patients (targets) weekly via session audio recordings and patient-report. We will optimize new Adhere.ly features and exercises, and our I/S blueprint during the trial and assess implementation outcomes post-implementation.

2.2

This is a feasibility trial and is not powered for hypothesis testing.

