Anxiety Severity	Patient	General Anxiety Disorder-7 (GAD-7) ^{40,41}	✓	✓
Depression Severity	Patient	Patient Health Questionnaire-8 (PHQ-8) ⁴²	✓	✓
Quality of Life	Patient	Health-Related Quality of Life (CDC HRQOL-14) ⁴³	✓	✓
Therapeutic Alliance	Patient	Working Alliance Inventory- Short Revised (WAI-SR) ⁴⁴		✓
Treatment Satisfaction	Patient	Client Satisfaction Questionnaire (CSQ-8) ⁴⁵		✓

Note. B=Baseline; 3M=3-Month Follow-Up.

Provider homework use, patient homework adherence, and treatment fidelity

Patient homework adherence will be assessed weekly on the day of their next session using a REDCap survey, a link to which will be sent via automated text-message and/or email reminders, or via telephone by study staff after 1 day of no response. The first 4 items of the Homework Rating Scale II (HRS II) will be used to measure patient homework adherence.⁴⁶ Session audio recordings will be observationally coded by independent coders blinded to study aims. Provider adherence and competence in reviewing, designing, and assigning homework (i.e., homework use) will be assessed using the Homework Adherence and Competence Scale (HAACS).⁴⁷ Provider general therapeutic and CBT-specific skills to appropriately deliver CBT will be assessed by the Assessment of Core CBT Skills (ACCS).⁴⁸

Optimization

We will iteratively optimize Adhere.ly and our implementation strategies during the feasibility trial based on user data, error reports, support requests, and data from routine feedback interviews conducted by Adhere.ly, LLC. We will address unanticipated problems and opportunities encountered during implementation, remove unnecessary components and I/S strategies, and improve processes and functionality. We will develop a clear set of procedures for optimization and keep a log of all changes made for reporting purposes, consistent with the Trials of Intervention Principles outlined by Mohr and colleagues.⁴⁹

Implementation

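### Provider homework use is to be compared by ANOVA with no covariate, although a baseline provider measure (ATHQ) is collected and could be prespecified; the gain is conditional and probably modest

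*Combined protocol and SAP*

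**What the plan says.** The Evaluation paragraph of section 16.1 treats two groups of outcomes differently. For clinical outcomes, "ANCOVA will be used to preliminarily assess-between group differences in clinical outcomes while co-varying for pre-treatment scores". For the homework outcomes, "ANOVA will be used to compare homework use and adherence", with no covariate and no unit of analysis stated.

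Section 2.1 gives the homework outcomes their standing: "We will assess homework use by providers and adherence of patients (targets) weekly via session audio recordings and patient-report". Two targets are named and neither is ranked above the other. Under section 5.2, provider homework use is scored on the HAACS by coders listening to session recordings.

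Section 5.2 (Recruitment of providers) has each provider complete, after consent, a "demographics questionnaire and the Attitudes Toward Homework Questionnaire (ATHQ"). Table 1 ticks the ATHQ at baseline and at 3 months. Section 5.2 (Treatment) then states that "providers will be informed of their assignment only after their first study-eligible patient has been enrolled". Section 16.1 assigns the ATHQ to no analysis. Its sentence on relations among study variables names only alliance and satisfaction.

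**The concern.** Apart from demographics, the ATHQ is the only provider measure that Table 1 lists at baseline, and it concerns the behaviour that the HAACS later scores. If attitude to homework predicts use of homework, a chance difference between arms in attitude carries over into the ANOVA estimate, and a covariate would remove that part. The number of providers is small enough for such imbalance to be common. Because the ATHQ is completed before the arm is disclosed, knowledge of assignment cannot have influenced it, so it is a legitimate covariate.

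At stake is the precision of a preliminary between-arm estimate, and what that estimate can tell the designers of Phase II. Leaving the covariate unspecified also leaves open the choice to adjust after the data have been seen.

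**Working it through.** The plan gives no SD, effect size, power or precision figure for homework use, so there is no figure of its own to reproduce.

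**Inputs**
- Providers: 50, randomized 25 to 25 (sections 1.1, 5.1, 11.1). Section 2.1 also gives a total of 30 beside the same 25 and 25; I used 50.
- Contributing providers, low case: each provider is asked to treat 3 patients (5.2) and 60 patients are planned, so 60/3 = 20 providers could supply them all. Providers with no uploaded recording have no HAACS score; recording is optional for patients and the upload benchmark is 70% (16.1).
- Correlation r between baseline ATHQ and the provider's HAACS score: not in the documents. Assumed range 0 to 0.5.
- Assumed: one summary score per provider, equal arms, two-sided 95% intervals, results in SD units of that score. Stratification by practice location is ignored.

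**Chance imbalance.** The difference in mean ATHQ between arms has SD √(2/n) for n providers per arm: √(2/25) = 0.28 SD, or √(2/10) = 0.45 SD. Under a normal approximation, an imbalance of 0.5 SD or more in either direction occurs about 8% of the time at 25 per arm and 26% at 10 per arm. It would move the ANOVA estimate by r × 0.5, which is 0.15 SD at r = 0.3 and 0.25 SD at r = 0.5.

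**Precision.** For one covariate in a randomized two-arm comparison of N providers, the variance ratio of ANCOVA to ANOVA is (1 − r²)(N − 3)/(N − 4). Examples: N = 50, r = 0.3 gives 0.91 × 47/46 = 0.93; N = 20, r = 0.2 gives 0.96 × 17/16 = 1.02. The equivalent number of providers is N divided by the unrounded ratio. The 95% half-width is t × √(4/N × ratio), with N − 3 degrees of freedom (N − 2 and ratio 1 for ANOVA).

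| Assumed r | Ratio, N = 50 | Equivalent providers | Half-width (SD) | Ratio, N = 20 | Equivalent providers | Half-width (SD) |
|---|---|---|---|---|---|---|
| ANOVA | 1 | 50 | 0.569 | 1 | 20 | 0.940 |
| 0 | 1.02 | 48.9 | 0.575 | 1.06 | 18.8 | 0.973 |
| 0.2 | 0.98 | 51.0 | 0.564 | 1.02 | 19.6 | 0.953 |
| 0.3 | 0.93 | 53.8 | 0.549 | 0.97 | 20.7 | 0.928 |
| 0.5 | 0.77 | 65.2 | 0.498 | 0.80 | 25.1 | 0.842 |

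**Break-even.** Setting the ratio to 1 gives |r| = √(1/(N − 3)): 0.15 at N = 50 and 0.24 at N = 20. Below these values adjustment loses precision.

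**Check.** Simulation with 20,000 runs per setting gave ratios of 1.023, 0.932 and 0.767 at N = 50, and 1.067, 0.966 and 0.799 at N = 20, for r = 0, 0.3 and 0.5. These agree with the formula.

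**The case against.** The strongest reply is that the plan is coherent as written. It adjusts clinical outcomes for their own pre-treatment scores. HAACS ratings come from treatment sessions, so homework use has no pre-treatment score, and ANOVA is the natural counterpart. The ATHQ is a self-reported attitude scale, not a baseline of observer-rated behaviour, and its 3-month administration suggests it was meant as a pre-post measure. All of this stands. A reader might infer an internal contradiction in 16.1 from the ANCOVA/ANOVA contrast; there is none.

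A reader might also infer that adjustment can only help. That does not follow: no correlation is given, and a weak covariate slightly widens the interval. The shortcut 1/(1 − r²), which gives 1.04, 1.10 and 1.33 times the providers at r = 0.2, 0.3 and 0.5, omits the lost degree of freedom. At 20 providers and r = 0.2 it reports a gain where the table shows a small loss.

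The consequence is limited as well. Section 2.2 says the trial is not powered for hypothesis testing, 16.1 rules out conclusions about effectiveness, and no feasibility benchmark is a between-arm contrast in homework use. Under provider randomization the unadjusted provider-level estimate is unbiased.

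Finally, the unstated unit of analysis probably matters more than the covariate. Sessions lie within patients and patients within providers, and a session-level ANCOVA would still treat them as independent. This stands too, so the fix has to settle the unit at the same time.

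What the reply does not remove is that a legitimate baseline measure is collected, has no stated use, and could be prespecified at little cost.

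**Conclusion.** The point holds as a modest, optional-to-advisable improvement. The homework-use comparison has no covariate, and baseline ATHQ is available and taken before the arm is disclosed. At 50 providers, adjustment changes the variance by between +2% (r = 0) and −23% (r = 0.5). At 20 contributing providers the range is +6% to −20%. These figures rest on assumed correlations, one score per provider and equal arms. The downside is one degree of freedom and a 2% to 6% loss of precision if ATHQ is unrelated to homework use.

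Three stronger readings are not supported. Homework use is not ranked above patient adherence: section 2.1 names both as targets. The omission does not bias the comparison. And the case does not extend to adding the patient's GAD-7 and PHQ-8 to the adherence analysis: the documents relate neither score to homework adherence, and the eligibility threshold of 10 restricts their range.

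**What to change.** In section 16.1, prespecify baseline ATHQ as a covariate for provider homework use. Use either an ANCOVA on one HAACS summary score per provider, with the summary defined, or a mixed model with a provider random effect, so that sessions and patients of one provider are not treated as independent. Keep the unadjusted estimate at the same unit as a check. Report the ATHQ-HAACS correlation with its confidence interval, so that Phase II can decide whether the covariate is worth carrying forward.

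The cost is a sentence or two in 16.1 and one degree of freedom. No new data, visits or instruments are needed. The amendment should be made before outcome data are examined by arm.
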